The intervention emphasizes three behavioral targets: a) providing resources to support breastfeeding through modeling, information, and feedback (tailored to maternal reported breastfeeding challenges and motivations); b) providing prompts to mother and partner to communicate about support strategies (tailored to parents' preferred support behaviors); and c) providing prompts for positive evidence-based coping strategies (tailored to parents' preferred coping activities). Exclusive breastfeeding as well as breastfeeding self-efficacy will be measured at 6 weeks and 6 months as primary outcomes. Secondary outcomes of coping behaviors and perceived partner support are the behavioral targets that are hypothesized to influence the primary outcomes of BSE and exclusive breast feeding and will also be measured at 6 weeks and 6 months. Because the intervention emphasizes coping strategies for managing stress, we hypothesize that baseline cortisol will act as a moderator for the intervention, with mothers experiencing elevated cortisol benefitting the most from the intervention.

In 2017, we conducted a small pilot study to test the feasibility of our HHL program. We enrolled 17 mothers and 10 partners to complete the baseline assessments and then randomly assigned them to the HHL group (n=8 mothers) or usual care (n= 8 mothers). Follow-up rates at 6-weeks postpartum were 94% for mothers and 90% for partners. Mothers and partners who completed the HHL intervention (n=12) rated the acceptability of the program on a five-point agreement scale. The majority of parents agreed or strongly agreed that the program was beneficial (83%) and that participating was manageable (91.7%). No parents opted to stop receiving messages during the six-week delivery.

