Investigating individual variability in intervention effectiveness. In the final aim of the proposal, we explore the extent by which subjective reports of stress and a biological indicator, namely hair cortisol levels, at baseline, and post intervention is associated with the mechanisms of change, as well as breast feeding rates. We hypothesized that higher levels of cortisol will be associated with lower levels of baseline positive coping, BSE, and partner support. Importantly, we also explore both self-reported stress, and hair cortisol levels as moderators of the effects of the intervention. The effects of any behavioral intervention vary significantly, and precision medicine approaches advocate that prevention and treatment strategies take seriously this variability (Insel, 2014). While the majority of this approach has been applicable in the context of oncology, it has important implications for psychological and behavioral research. Consistent with past studies, suggesting that interventions may be particularly useful for those with higher vulnerability at baseline (Blow et al., 2009; Snider et al., 2018), we hypothesized that the intervention would have the biggest impact on mothers with the highest levels of perceived stress and cortisol levels.

We look specifically at subjective reports of stress and hair cortisol due to a large body of research demonstrating intriguing relations between neuroendocrine mechanisms and failed lactation, as well as perinatal mood disorders (Stuebe et al., 2012). Elevated cortisol in the perinatal period is associated with the development of mood disorders (Magiakou et al., 1996; Nierop, Bratsikas, Zimmermann, & Ehlert, 2006a; Nierop, Bratsikas, Zimmermann, & Ehlert, 2006b). In addition, stress is associated with non-responsive feeding styles (Hurley, Black, Papas, & Caulfield, 2008) and undesired weaning (Sjolin, Hofvander, & Hillervik, 1977). Causal evidence demonstrating that chronic stress exposure leads to deficits in maternal care and increases in anxiety and impaired lactation were found in rodent models (Murgatroyd et al., 2015).

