Traditional methods of assessing cortisol levels via saliva, urine or plasma are cumbersome, requiring multiple assessments in order to ascertain long term exposure, thus increasing participant burden, attrition and limiting its application during the post-partum period. Hair cortisol provides longer retrospective calendar of exposure to stress, thus has the potential to be a non-invasive biological variable that can be collected with ease, making it an excellent candidate for assessing chronic stress in new mothers. Hair cortisol level is associated with traditional salivary cortisol levels throughout pregnancy (D'Anna-Hernandez, Ross, Natvig, & Laudenslager, 2011; Kirschbaum, Tietze, Skoluda, & Dettenborn, 2009a), and is related to self-report levels of stress among pregnant women (Kalra, Einarson, Karaskov, Van Uum, & Koren, 2007). At the same time, a significant body of research demonstrates that self-reports of stress do not always correlate with biological indicators such as cortisol (Kalra et al., 2007; McLennan, Ihle, Steudte-Schmiedgen, Kirschbaum, & Kliegel, 2016; Milam, Slaughter, Verma, & McConnell, 2014), thus begging the question of which measure may be best for assessing stress in new mothers. By using both self-report measures of stress, as well as hair cortisol as a biological marker, we are able to examine their relations to one another as well as their role in moderating the effects of the intervention. Thus, findings from the current study has the ability to both provide further evidence for hair cortisol as a biomarker of exposure to stressful life events during the prenatal period, as well as its feasibility in predicting the efficacy of interventions.

II. METHODS

A. Study Population

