Hypothesis 1: Participants randomly assigned to the intervention will report higher breastfeeding self-efficacy and exclusive breastfeeding at six weeks and six months postpartum compared to those assigned to usual care.

Aim 2: Assess whether improved coping with stress (as measured by self-reports), and partner support (as measured by partner and self-report) are mechanisms for the intervention.

Hypothesis 2: Participants randomly assigned to the intervention will report increased positive coping behaviors and higher perceived partner support at six weeks and six months postpartum compared to participants assigned to usual care.

Aim 3: Investigate relationships among levels of hair cortisol, stress (e.g. as indexed by subjective reports of stress) and resilience (social support and positive coping) factors.

Hypothesis 3: Hair cortisol levels measured immediately postpartum will be positively associated with symptoms of depression, anxiety, and stress, and negatively associated with perceived partner support and effective coping.

Aim 4: Investigate hair cortisol levels as a biological indicator of susceptibility (e.g. moderator) to intervention effects.

Hypothesis 4: Mothers who have moderate-high hair cortisol levels will benefit most from HHL.

C. Study Variables

A summary of the measures proposed is provided in the table below.

Construct	Measure	0-2 days postpartum		6 weeks postpartum		6 months postpartum	
		mom	partner	mom	partner	mom	partner
Breastfeeding	Index of breastfeeding status	x		x		x	
Self-efficacy	Breastfeeding self-efficacy scale short form	x	x	x	x	x	x
Coping Behavior	brief COPE	x	x	x	x	x	x
Partner Support	Postpartum Partner Support Scale	x	x	x	x	x	x
	Social provisions checklist	x	x	x	x	x	x

Mood/Stress	Edinburgh Postnatal Depression Scale	x	x	x	x	x	x
	Depression, Anxiety, and Stress Scale	x	x	x	x	x	x
	Maternal Mood Screener	x	x	x	x	x	x
Sleep Quality (cortisol covariate)	Pittsburgh Sleep Quality Index	x					
Acceptability & Adherence	HHL acceptability scale Participant adherence			x	x	x	x

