Hair cortisol. To provide convergent validity of the DASS-21 and other stress scales, we are collaborating with [name] of Claremont McKenna College to analyze hair samples and the correlation of this known biomarker of cortisol to the mother's stated stress levels. We will share study ID number, deidentified hair samples, hair histories, and scores on coping behavior, partner support, mood/stress, and sleep quality index scales with [name] for comparative analysis with hair cortisol levels. Hair cortisol measurement procedures will follow validated methods (Dettenborn et al., 2010; Stalder & Kirschbaum, 2012). Hair cortisol collection is not required for participation in this study. All mother's with at least 3 cm of hair who enroll in "Happy, Healthy, Loved" may opt to contribute a hair sample. The study staff member who explains the study and obtains the informed consent will collect the hair sample at the time the baseline questionnaires are obtained. At baseline, a small amount (15-30 mg) of hair from the posterior vertex of the head will be collected. Hair strands will then be cut into 3 cm segments, which based on human scalp hair grows at approximately 1 cm per month (Kirschbaum, Tietze, Skoluda, & Dettenborn, 2009b), so each of the 3 cm sample will indexed cortisol output during the three trimesters of pregnancy (D'Anna-Hernandez et al., 2011; Kirschbaum et al., 2009). If hair is less than 9 cm long, the analysis will include only the number of 3 cm segments available. The wash procedure and steroid extraction will be undertaken using high performance liquid chromatography-mass spectrometry (Gow, Thomson, Rieder, Van Uum, & Koren, 2010). Additionally, because washing, hair straightening or dyeing, and styling products may affect HCC (Gow et al., 2010), mothers will be asked about their hair histories to use as covariates in analysis along with hair sample. Hair histories include questions related to hair color, salon treatments, sunlight exposure, use of hair products, medications, creams, and hair pieces, style and indoor tanning habits. The samples will be sent to [name] of Claremont McKenna College for analysis.

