The intervention's impact on the study's primary outcomes will be evaluated using intent-to-treat analysis with multiple imputation for missing follow up cases. Outcomes, adjusting for baseline variables, will be analyzed using ANCOVA for continuous variables (self-efficacy, partner support, and coping) and logistic regression for categorical variables (exclusive breastfeeding). To examine the extent in which increased partner support, and lower levels of stress would explain the effects of the intervention, two criteria will be used to establish whether there is statistically significant mediation in the model (MacKinnon, Lockwood, Hoffman, West, & Sheets, 2002; MacKinnon, Fairchild, & Fritz, 2007) including the joint significance of paths a (i.e., the path from predictor to mediator) and b (i.e., the path from mediator to outcome variable) and the asymmetric distribution of the product confidence interval test for the product ($a*b$) of the coefficients a and b , which have both shown the best combination of power and avoidance of type 1 error compared to 12 alternative tests of mediation (MacKinnon et al., 2002; MacKinnon et al., 2007).

We will use the regression-based approach described by Hayes to develop models that allow us to evaluate mediation (Hayes, 2008). The bootstrapping resampling method available in this approach provides an opportunity to run analyses that will approximate the sampling distribution to obtain confidence intervals (CIs) when variables are not normally distributed. With regards to aims 3 and 4, regression (logistic regression for dichotomous outcome variables) analyses controlling for relevant covariates will be used to examine relations between hair cortisol levels and partner support, coping, self-efficacy, and breastfeeding rates. Because both high and low levels of cortisol have been indicated as signs of dysregulation (Miller, Chen, & Zhou, 2007), a quadratic term will be added to the model to examine non-linear relationships. In addition, to these analyses, we will also use the mediation approach described above to explore the extent to which maternal mood may mediate the relations between cortisol and breastfeeding behaviors.

III. REFERENCES

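### Aim 4 asks whether cortisol moderates the HHL effect, but the analyses stated for Aims 3 and 4 have no arm-by-cortisol term, so as written they cannot test Hypothesis 4

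*Combined protocol and SAP*

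**What the plan says.** Section II.B states Aim 4 as "Investigate hair cortisol levels as a biological indicator of susceptibility (e.g. moderator) to intervention effects". Hypothesis 4 gives it a direction: "Mothers who have moderate-high hair cortisol levels will benefit most from HHL". The Introduction repeats the idea three times: "we hypothesize that baseline cortisol will act as a moderator for the intervention" where the outcomes are set out, "we also explore both self-reported stress, and hair cortisol levels as moderators of the effects of the intervention" under individual variability, and, of self-reported stress and hair cortisol together, "their role in moderating the effects of the intervention".

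Section II.E is the only statistical section. It deals with Aims 3 and 4 in one sentence: regression, logistic for two-category outcomes, with unspecified relevant covariates, "will be used to examine relations between hair cortisol levels and partner support, coping, self-efficacy, and breastfeeding rates". It then adds a quadratic cortisol term, because both high and low levels may indicate dysregulation, and a mediation analysis from cortisol through maternal mood to breastfeeding.

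On measurement, section II.C says "Hair cortisol collection is not required for participation in this study" and limits donation to mothers with at least 3 cm of hair. It adds "If hair is less than 9 cm long, the analysis will include only the number of 3 cm segments available". Each donor therefore supplies one to three segment values, and II.E does not say which is analysed.

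**The concern.** Aim 3 is about association, and the sentence in II.E fits it. Aim 4 is about a difference in arm effects across cortisol levels, which needs a term combining arm and cortisol, or arm effects estimated within cortisol strata. II.E has neither, and gives no cut-point for the moderate-high group in Hypothesis 4.

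Two things are at stake. First, a cortisol coefficient from the stated model could be reported as support for Hypothesis 4 when it shows only that cortisol predicts the outcome; it can also be null when moderation is real. Second, if the interaction is added after the data are seen, the segment, outcome, visit and functional form can all be chosen with the results in view.

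**Working it through.** **1. What the stated coefficient estimates.** Write the outcome as b0 + b1·arm + b2·cortisol + b3·arm·cortisol, with arm 0 for control and 1 for HHL. Hypothesis 4 concerns b3. With 1:1 randomisation and cortisol measured at baseline, a model without the product term estimates the average of the two arm-specific cortisol slopes: (b2 + (b2 + b3))/2 = b2 + b3/2. Control/HHL slopes of 0/0.4 and of 0.2/0.2 both average 0.2, although only the first pair is moderation. Slopes of -0.2/+0.2 average zero, although moderation is just as strong as in the first pair. Adding arm as a covariate does not change this.

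**2. Illustration, continuous outcome.** Assumptions: residual SD 1, standardised cortisol, 1:1 arms, N = 128, two-sided 5% tests, 10,000 simulated trials per row. The slopes are assumed; the documents give none. The stated model is cortisol plus cortisol squared.

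| Slopes (control/HHL) | Moderation? | Stated cortisol term rejects | Arm × cortisol rejects |
|---|---|---|---|
| 0/0.4 | yes | 57% | 60% |
| 0.2/0.2 | no | 59% | 5% |
| -0.2/+0.2 | yes | 5% | 60% |
| 0/0 | no | 5% | 5% |

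The quadratic term does not fill the gap. In a separate run with pure moderation of 0.5 SD per SD and no average slope, it rejected in 6.9% of trials, against 76% for the interaction.

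**3. Illustration, exclusive breastfeeding.** Logistic model, N = 128, control rate 44.4% (borrowed from the US three-month figure in the Introduction), log-odds slopes 0/0.69, 0.35/0.35 and -0.35/+0.35. The cortisol term rejects in 42%, 46% and 5%; arm × cortisol rejects in 44%, 5% and 46%.

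**4. The plan's own sample size.** Section II.A states 64 per arm for 80% power at alpha .05 and gives no numerical effect size. Assuming d = 0.5 and a two-sided test, the normal formula gives 63 per arm and the exact t test gives 80.1% power at 64. The figure reproduces, but it is for the arm main effect; nothing is stated for Aim 4.

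**5. Precision once the interaction is added.** Each arm's slope has variance of about 1/(N/2), so the slope difference has SE of about 2/√(N-4).
- N = 128: SE = 2/√124 = 0.180; 95% half-width = 1.98 × 0.180 = 0.36.
- Power = Φ(difference/SE - 1.96). For 0.4: Φ(0.27) = 60%. For 0.25: Φ(-0.57) = 28%, with other calculations giving 27% to 29%. For 0.2: Φ(-0.85) = 20%.
- With hair from 75% or 50% of completers (assumed; N = 96 or 64), half-widths are 0.42 and 0.52. Power falls to about 47% and 33% at 0.4, and 23% and 17% at 0.25.

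A difference of 0.4 is large: it moves the HHL effect by 0.8 SD between mothers 1 SD below and 1 SD above mean cortisol, against the 0.5 SD main effect that reproduces the sample size.

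**6. Choices left open.** Up to 3 segments × 2 primary outcomes × 2 visits = 12 linear interaction coefficients, before any choice of cut-point, scale or averaging. With no moderation, the chance that at least one has p < .05 is 1 - 0.95^12 = 46% if they are independent. It is about 21% to 40% under assumed correlations (0.3 to 0.9 between segments, 0.3 to 0.7 between outcomes). That simulation treated all outcomes as continuous, so it is a guide only.

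**7. Shape.** The plan's reason for the quadratic applies to moderation too. Under an assumed purely U-shaped moderation at N = 128 (0.4 per SD of the quadratic), the linear interaction rejects in 8% of trials and the quadratic interaction in 52%.

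**The case against.** The best defence is that II.E names a method and not a closed model. It says the method serves Aim 4, Aim 4 itself says moderator, the covariates are left open, and the title of the cited regression text covers moderation. On that view the model is under-specified, not wrong. Part of this stands: the intent to study moderation is plain, and a reader who inferred that the sponsor had dropped moderation, or had knowingly chosen main-effect regressions as its test, would go beyond the documents. But none of these points supplies a model. A covariate adjustment for arm is not an interaction, and II.E invokes the cited text for mediation only.

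It is also fair that the contrast in the simulation follows from the slopes chosen. It illustrates the algebra in step 1 and says nothing about the effects this trial will find.

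Three further readings are tempting and not supported:
- That 12 is the maximum number of choices. It counts linear coefficients on single segments for the two primary outcomes only; cut-points, averaging, a log scale, the quadratic interaction, partner support and coping would add more.
- That a linear interaction on one particular segment, outcome and visit is the only proper test. The documents give both primary outcomes and both visits equal standing, and their quadratic rationale argues against assuming linearity.
- That self-reported stress is an equal gap. It appears as a moderator only in the Introduction, in exploratory terms; Aim 4 and Hypothesis 4 name hair cortisol alone. II.E uses lower stress only as a mediator, so this is a secondary point.

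**Conclusion.** The point holds. A numbered aim with a directional hypothesis has no stated analysis able to address it, and this can be read directly from sections II.B and II.E without any assumption. The rejection rates and power figures do rest on assumptions: the slopes, residual SD 1, the borrowed control rate and the hair uptake. They show the kind of error that could follow, not its likelihood here. It should be fixed before outcome data are examined. It does not touch Aim 1, and Aim 3 is served by the regressions as written. A reader might infer that adding the interaction would give a well-powered test; step 5 shows that it would not.

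**What to change.** In section II.E, separate Aim 4 from Aim 3 and add for Aim 4 a model of each primary outcome (linear for self-efficacy, logistic for exclusive breastfeeding) on arm, continuous baseline cortisol and arm × cortisol, adjusted for the baseline outcome and the hair covariates. Because the plan already has a quadratic, either include arm × cortisol squared as well, for example as a joint test with the linear interaction, or state in advance that only the linear interaction tests Hypothesis 4.

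The sponsor should fix the cortisol measure, the outcome and the visit for that test before seeing data. The segment nearest the scalp (which every donor has), the BSES-SF and six weeks are examples, not requirements. Report the other interactions as estimates with 95% confidence intervals, and label Aim 4 exploratory. An arm × baseline stress model can be listed as a further exploratory analysis.

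The cost is a few sentences and no new data. The downside is low precision, and lower still with partial hair uptake, so the text should say that a null interaction would not rule out moderation.
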